## **9.1. Toxicity**

Only toxicities considered related to HXTC and/or VOR will be managed directly by this protocol.

Participants will be monitored closely for adverse effects. Toxicities will be characterized in terms including duration, intensity, and time to onset. Safety endpoints will include all adverse experiences, in addition to laboratory safety assessments and vital signs.

For this study, the hemoglobin will be graded using version 2.1 [July 2017] of the DAIDS Table for Grading the Severity of Adult and Pediatric Adverse Events where a hemoglobin <11 mg/dl for men and <10.5 for women will be considered a Grade 1 toxicity.

### **9.1.1. Grade 1 or 2 Toxicity**

Participants who develop a Grade 1 or 2 AE or toxicity that occurs following an HXTC infusion or VOR dosing that is thought to be possibly, probably, or definitely related to HXTC and/or VOR should be discussed with the study team.

In the event of a grade 1 toxicity related to hemoglobin or anemia the study team should be contacted to guide the elimination of research labs as needed to avoid a grade 2 toxicity related to hemoglobin.

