In this proposed study, participants will receive 10 doses of 400 mg VOR over a 30 day period, then no VOR for 4 weeks. They will then receive a second cycle of 10 doses of 400mg VOR over another 30 day period, for a total of 20 doses. Each participant will receive a total of 5 HXTC infusions; 2 infusions will be administered in the first 4 week cycle and 3 administered in the second 4 week cycle. In our previous study with VOR, most participants exhibited a 15%–35% transient decline in platelet count after 4 weeks of 3 daily doses each week. However, only one participant's platelet count reached grade 1 toxicity level. No other clinical events or drug-related AEs were observed. Given we now propose to administer fewer doses, over a shorter time (20 doses over 3 months), significant toxicity seems unlikely.

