## **5.5. Premature Termination or Suspension of Study**

### **5.5.1. Study Treatment Stopping Rules or Permanent Treatment Discontinuation**

A participant will not receive VOR and/or HXTc infusions if any of the following occurs:

- Pregnancy of study participant
- Treatment related  $\geq$  Grade 3 adverse event
- Requirement for prohibited concomitant medications
- Inability to complete treatments as defined in the protocol
- Request by participant to terminate study treatments
- Clinical reasons believed life-threatening by the PI or designee
- Hematologic dose-limiting toxicity defined as any confirmed toxicity  $\geq$  Grade 2, that cannot clearly be attributed to another reversible cause other than VOR
- Development of a dose-limiting toxicity
- HIV RNA  $> 150$  copies/mL on two consecutive determinations.

Participants who prematurely discontinue study treatment will move to Step 6, Visit 23 and will be followed through Visit 24. See section 5.4, Participant Withdrawal, for details on study procedures to be completed.

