#### **8.1.2. Clinical Laboratory Procedures**

These laboratory evaluations will be conducted primarily at one of the clinical site laboratories available to the research team. Details of specimen collection are found in the Lab Procedures Manual for this study.

At designated visits, the study PI (or designee) assesses the clinical events and the laboratory test results and determines whether the participant can receive VOR doses or HXTC infusions. If values are outside the study reference range, the PI (or designee) determines if the abnormal value is clinically significant and if study treatments can continue. Report all abnormal laboratory values that the investigator deems clinically significant as AEs.

All participants will have safety labs (CBC with differential and chemistries) done throughout the study to monitor for any adverse events due to the administration of VOR and HXTC therapy. Labs that are abnormal and meet grading standards per Division of AIDS (DAIDS) Table for Grading the Severity of Adult and Pediatric Adverse Events, Version 2.1. [July 2017], will be re-assessed based on these initial parameters.

Blood specimens will be collected and evaluated at either UNC McLendon Hospital Lab or LabCorp.

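### Section 5.5.1 mandates a stop for confirmed Grade 2 or higher hematologic toxicity not clearly due to another reversible cause, the laboratory and pre-dose rules allow treatment to continue by judgement, and no passage says which prevails

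*Combined protocol and SAP*

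**What the plan says.** Section 5.5.1 is worded as mandatory. It opens with "A participant will not receive VOR and/or HXTc infusions if any of the following occurs", and one listed item is "Hematologic dose-limiting toxicity defined as any confirmed toxicity" at or above "Grade 2, that cannot clearly be attributed to another reversible cause other than VOR". The item therefore has three conditions: the toxicity is confirmed, it is Grade 2 or higher, and no other reversible cause clearly explains it.

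Other sections reach the same event:

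- Section 8.1.2: when a laboratory value is outside the study range, "the PI (or designee) determines if the abnormal value is clinically significant and if study treatments can continue".
- Sections 7.3.3.7 (Visit 13) and 8.1.1.4: ANC, platelets and hemoglobin are among the pre-dose laboratory values. A failed value may be repeated once. If it is still outside the limits, the participant may go on to dosing when the PI documents the value as not clinically significant and the protocol and/or safety committee approves.
- Section 9, opening paragraph: criteria for interrupting treatment are mandated only for toxicities rated possibly, probably or definitely related.
- Section 9.1.1: a Grade 1 or 2 event "that is thought to be possibly, probably, or definitely related to HXTC and/or VOR should be discussed with the study team". For Grade 1 hemoglobin it also asks that research samples be cut as needed "to avoid a grade 2 toxicity related to hemoglobin". It gives no action once Grade 2 is reached.
- Sections 9.1.2 and 9.1.3: no further doses after a related Grade 3 or Grade 4 event.

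Section 10.4 replaces anyone who does not receive the full study treatment. Section 10.5 leaves it to the protocol team to determine whether replacements are needed.

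**The concern.** A stopping rule works only if staff reach the same decision whichever section they open. Here one section removes the decision and others hand it to the PI or a committee. Section 9 is where staff would look when managing a toxicity. It repeats the Grade 3 stop that 5.5.1 also contains, but not the Grade 2 hematologic stop, and it does not point to 5.5.1.

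Cytopenias are one of the three main categories of VOR toxicity named in section 2.2.5, so the rule concerns an effect that the protocol itself expects from the drug class. Two things are at stake: whether a participant is dosed again after a toxicity that one section treats as ending treatment, and whether that participant counts among the 12 fully treated or is replaced.

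**Working it through.** The point rests on comparing passages, so the check takes one event through each of them.

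**Case A.** At Visit 13, after ten VOR doses, a participant has a Grade 2 fall in a hematology value. The single permitted repeat confirms it, the PI rates it possibly related to VOR, and no other reversible cause is clear. Two assumptions are needed. First, the repeat counts as confirmation, because 5.5.1 does not define the word. Second, the Grade 2 value lies outside the pre-dose limit. For hemoglobin the second follows from the text: section 9.1 starts Grade 1 below 11 (men) and 10.5 (women), under the pre-dose limits of 12 and 11 g/dL. For ANC and platelets the grade cut-offs are not printed.

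- 5.5.1: all three conditions are met, so no further VOR and/or HXTC.
- 8.1.2: the PI may let treatment continue.
- 7.3.3.7 and 8.1.1.4: the participant may proceed with documentation and committee approval.
- 9.1.1: discuss with the study team; silent on dosing.
- 9.3 (discontinuation): gives no criterion.

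The overlap is not empty and no order of precedence is given. The repeat result that completes the 5.5.1 condition also opens the committee route. At laboratory checks between pre-dose visits, the discretion comes from 8.1.2 alone. The waiver at Visit 6 is not part of the conflict, because it precedes the first VOR dose.

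**Case B.** Take the same event, rated unlikely on the five-level scale in section 9.2.4, still with no clear alternative cause. Section 5.5.1 stops treatment. The opening of section 9 mandates nothing, and 9.1.1 does not apply. The two attribution tests can therefore separate.

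Attribution can be a real question for hemoglobin. The maximum blood volumes for Visits 7 to 13 sum to 60 + 105 + 45 + 45 + 25 + 60 + 60 = 400 mL, a possible other reversible cause.

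**Size.** One participant in 12 is 1/12 = 8.3%. Section 10.4 gives one-sided 95% upper limits of 22% for 0 of 12 and 34% for 1 of 12. Both reproduce:

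- 0 of 12: 1 − 0.05^(1/12) = 0.221.
- 1 of 12: (1 − p)^12 + 12p(1 − p)^11 = 0.05 gives p = 0.339.

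A Grade 2 event is not itself a primary safety event, since section 10.2.1.1 counts Grade 3 or higher. The link is conditional: a participant who continues could later reach Grade 3, and one who is stopped has no further exposure.

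**Frequency.** Section 2.2.5 says of the earlier VOR study that "most participants exhibited a 15%–35% transient decline in platelet count after 4 weeks of 3 daily doses each week". From the pre-dose floor that is 125,000 × 0.85 = 106,250 to 125,000 × 0.65 = 81,250 per mcL. No Grade 2 platelet cut-off is printed, so these values cannot be graded from the documents. The next sentence of that section says only one participant's platelet count reached Grade 1.

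**The case against.** The strongest reply is that 5.5.1 is the specific, mandatory rule and simply governs. Staff can obey 9.1.1 and 5.5.1 together by discussing the event and stopping treatment. The hemoglobin sentence in 9.1.1 even fits the idea that Grade 2 carries a consequence stated elsewhere. This stands for 9.1.1. A reader might infer that 9.1.1 authorises continued dosing, but the text does not say so; it is silent.

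The reply is weaker for the other passages. Section 8.1.2 covers a broader class, any out-of-range value, and its mention of re-assessing gradable values could be read as the step towards confirmation. But it expressly addresses whether treatment continues, with no grade ceiling. The Visit 13 route expressly allows progress to dosing after a failed repeat. Section 7.4.3 says participants who fail the safety requirements receive no further doses, but it does not mention the committee route, so it does not settle precedence.

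On attribution, a cytopenia after VOR with no clear alternative cause would ordinarily be rated at least possibly related. Case B is therefore probably rare, though the wording allows it.

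On consequences, the primary safety endpoint and the two-participant suspension trigger both require Grade 3 or higher, and replacement applies to incomplete treatment for any reason. That limits the effect on the analysis but does not remove the conflict over dosing.

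**Conclusion.** The inconsistency is real but narrow. It concerns confirmed hematologic toxicity at Grade 2 that is not clearly due to another reversible cause. For that event, 5.5.1 requires a stop, while 8.1.2 and, at Visit 13, sections 7.3.3.7 and 8.1.1.4 give express discretion to continue. Section 9 adds to the uncertainty by omission and by a different attribution test.

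Two further inferences are not supported. First, not every confirmed Grade 2 hematologic event stops treatment under 5.5.1, because of its attribution exception. Second, the platelet falls do not show that Grade 2 events are likely. Section 2.2.5 reports one participant at Grade 1 for platelets and, across the earlier intermittent-dosing studies, nothing above Grade 1 except one episode of Grade 2 fatigue. Hemoglobin margins at entry measure distance to Grade 1, not Grade 2.

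No event rate is claimed. If a case occurs, it affects one participant in 12 (8%), that person's further dosing, and replacement under section 10.4. The conclusion assumes that no document outside the protocol, such as a site procedure, sets precedence.

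**What to change.** Reconcile sections 5.5.1, 7.3.3.7, 8.1.1.4, 8.1.2 and 9 (opening paragraph and 9.1.1):

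- State which passage prevails for confirmed Grade 2 hematologic toxicity.
- Use one attribution test throughout and say what counts as confirmed.
- Add cross-references, so that the laboratory, pre-dose and toxicity sections all lead to the same rule.

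Which clinical rule applies is for the sponsor and the SMC to decide. Once a single rule exists, there is no need to record which passage was applied to each event, and replacement under section 10.4 then follows from the same rule for everyone. The cost is a clarification of a few sentences, with no added procedures or participants.

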### **9.1.2. Grade 3 Toxicity**

For participants who develop a Grade 3 AE that occurs following an HXTC infusion or VOR dosing not specifically discussed below that is judged by a site investigator to be at least possibly study treatment-related, the protocol team must be notified within 24 hours. Participants with a study treatment-related Grade 3 AE will not receive any additional doses of study treatment/product. Participants experiencing Grade 3 AEs should be followed closely and if the AE does not return to Grade  $\leq$  2 within 2 weeks, the protocol team should again be notified within 24 hours.

For participants who experience a Grade 3 AE that is judged not related to the study drug by the investigator or designee, continued study participation is at the discretion of the principal investigator in consultation with the protocol team.

### **9.1.3. Grade 4 Toxicity**

For participants who develop a Grade 4 AE that occurs following an HXTc infusion or VOR dosing not specifically discussed below that is judged by a site investigator or designee to be at least possibly study treatment-related, the protocol team must be notified within 24 hours. Participants with a study treatment-related Grade 4 AE will not receive any additional doses of study treatment/product. Participants experiencing Grade 4 AEs should be followed closely with additional clinical assessments and laboratory testing as clinically indicated. If the AE does not return to Grade ≤ 2 within 2 weeks, the protocol team should again be notified within 24 hours.

#### **9.1.4. HXTc Infusion-related Toxicities**

Infusion reactions should be graded according to the criteria for acute systemic allergic reaction located in the Division of AIDS (DAIDS) Table for Grading the Severity of Adult and Pediatric Adverse Events, Version 2.1. [July 2017], which can be found on the DAIDS RSC Web site: <http://rsc.tech-res.com/safetyandpharmacovigilance/>.

These reactions may manifest with signs and symptoms that may include, but are not limited to fever, chills, headache, rash, pruritus, arthralgia, hypo- or hypertension, bronchospasm, or other symptoms.

##### **9.1.4.1. Grade 1 or 2 Local or Systemic Reactions**

Local reactions of mild (Grade 1) or moderate (Grade 2) severity will usually resolve spontaneously. If needed, they may be managed with local application of cold packs, oral acetaminophen, oral non-steroidal anti-inflammatory agents, or a combination of these measures as appropriate.

##### **9.1.4.2. Grade 3 or 4 Local or Systemic Reactions**

For severe (Grade 3) or potentially life-threatening (Grade 4) local reactions, the protocol team must be notified within 24 hours. For Grade 4 local reactions, definitive medical and/or surgical intervention should be undertaken as appropriate. Further infusions should not be administered prior to consultation with the core protocol team.

#### **9.1.5. Systemic Reactions**

The protocol team should be contacted within 24 hours for any non-local Grade 3 or 4 AE thought definitely, possibly, or probably related to study treatment. Additional study product should not be administered prior to consultation with the

protocol team. For severe infusion (Grade 3 or 4) reactions, appropriate medical therapy including epinephrine, corticosteroids, intravenous antihistamines, and oxygen should be available for use in the treatment of such reactions. Participants should be carefully observed until the complete resolution of all signs and symptoms. In each case of an infusion reaction, the site investigator should institute treatment measures according to the best available medical practice.

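### Section 5.5.1 ends treatment after any related Grade 3 or higher event, while 9.1.5 and 9.1.4.2 only hold product until consultation, and nothing says which prevails

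*Combined protocol and SAP*

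**What the plan says.** Section 5.5.1 is headed "Study Treatment Stopping Rules or Permanent Treatment Discontinuation". Its operative sentence is "A participant will not receive VOR and/or HXTc infusions if any of the following occurs", and the list that follows includes a treatment-related adverse event at or above Grade 3. The section has no exception, no consultation step and no reference to section 9. Participants who stop treatment go to Visit 23 and are followed through Visit 24.

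Section 9.1.2 says "Participants with a study treatment-related Grade 3 AE will not receive any additional doses of study treatment/product", and section 9.1.3 says "Participants with a study treatment-related Grade 4 AE will not receive any additional doses of study treatment/product". Each opens with a limit on its scope: 9.1.2 applies to Grade 3 events "not specifically discussed below that is judged by a site investigator to be at least possibly study treatment-related", and 9.1.3 has the same limit for Grade 4.

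Section 9.1.4.2 says "Further infusions should not be administered prior to consultation with the core protocol team". Its heading names local and systemic reactions, but its text deals only with local ones. It sets no relatedness condition and does not mention VOR.

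Section 9.1.5 is headed as a section on systemic reactions. It requires contact with the protocol team within 24 hours for "any non-local Grade 3 or 4 AE thought definitely, possibly, or probably related to study treatment", and withholds study product until that team has been consulted. Like 9.1.4.2, it states no permanent stop and does not refer to 5.5.1.

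**The concern.** A related Grade 3 or 4 event appears to meet two different rules: treatment ends under 5.5.1, but is paused pending a discussion under 9.1.5 or 9.1.4.2. A hold that lasts only until consultation has little purpose if product can never be given again, because each of the two sections already carries a separate 24-hour notification duty. So the natural inference is that dosing may resume.

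Three things depend on which rule is applied:

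- **Re-exposure.** In a phase I trial with safety as a primary objective, this is the main stake.
- **Replacement.** Section 10.4 replaces anyone who does not receive the full study treatment through Step 6. Section 10.5 also gives the protocol team the decision on whether replacements are needed.
- **The second reservoir measurement.** Section 7.5 has the Visit 23 leukapheresis done on everyone who completed all dosing visits, but leaves it to the investigator or study team when a participant terminates early. That sample supplies the post-treatment value for the primary endpoint in 10.2.1.2.

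**Working it through.** The plan gives no figure to reproduce here. The check is a comparison of scope and consequence by type of event.

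| Event, Grade 3 or 4 | 5.5.1 | 9.1.2 / 9.1.3 | 9.1.4.2 | 9.1.5 |
|---|---|---|---|---|
| Non-local, related, not an infusion reaction (e.g. a laboratory toxicity) | Stop | No more doses, unless 9.1.5 counts as discussing it | Does not apply | Hold until consultation, on its literal wording |
| Systemic infusion reaction, related | Stop | Gives way to 9.1.5 | Named in heading, not in text | Hold until consultation |
| Local reaction, related | Stop | Gives way to 9.1.4.2 | Hold infusions until consultation | Does not apply |
| Local reaction, not related | Does not apply | Stop sentence does not apply | Hold infusions until consultation | Does not apply |

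**Step 1: 9.1.2 and 9.1.3 against the reaction sections.** The opening limit lets both sections give way to later text. That reconciles them with 9.1.4.2, and with 9.1.5 as far as infusion reactions are concerned.

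**Step 2: the reach of 9.1.5.** Its literal scope is every related non-local Grade 3 or 4 event, whatever the cause. If the opening limit is applied to that scope, 9.1.2 and 9.1.3 are left with little beyond related local events that are not HXTC reactions. The limit therefore works sensibly only if 9.1.5 is confined to infusion reactions, and 9.1.5 does not say that it is.

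**Step 3: 5.5.1 against the reaction sections.** The limit does not appear in 5.5.1. In each of the first three rows, 5.5.1 stops treatment while a section 9 hold also applies, at least on its wording. In the fourth row there is no conflict, because 5.5.1 requires a treatment-related event.

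**Step 4: how often the rule might be tested.** With n = 12 (section 10.1), independent participants and a common true rate p of related Grade 3 or higher events, the chance of at least one affected participant is 1 − (1 − p)^12. The documents give no expected rate, so p is assumed:

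- p = 1%: 1 − 0.99^12 = 0.11
- p = 5%: 1 − 0.95^12 = 0.46
- p = 10%: 1 − 0.90^12 = 0.72

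These are chances that the question arises at all. They are not chances that a participant is managed inconsistently.

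**The case against.** The strongest defence is that the sections can be followed in sequence: hold, notify, consult, and then apply 5.5.1 if the event is confirmed as related. Section 9.1.5 speaks of events thought to be related, 5.5.1 of events that are related, and section 10.5 has the protocol team assess relatedness. This is coherent, but no section states it. Nor does the text support the distinction: the opening of section 9 sets the management threshold at possibly related or more, which is the same range that 9.1.5 uses.

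A second defence is that 9.1.5 is about reactions. Its heading, its position after the section on infusion toxicities and most of its content point that way. This stands as a likely intention, and on that reading 9.1.2 and 9.1.3 keep a real role. It still leaves 5.5.1 in conflict with 9.1.5 for infusion reactions.

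Several limits on impact also stand. This is a single-site trial with one protocol team, and that team hears of every such event within 24 hours. Replacement is not purely automatic, given 10.5. The safety endpoint in 10.2.1.1 is the occurrence of at least one related Grade 3 or higher event, so the affected participant generally counts whether or not dosing continues. The exception is a Grade 3 infusion reaction lasting less than 48 hours, which the endpoint excludes and for which 5.5.1 has no matching exception. Reported experience is also mild: section 2.1 records no treatment-related events at the lower cell dose, and section 2.2.5 records nothing above a single Grade 2 fatigue in the prior VOR studies. Rates of 5% or 10% may therefore be too high. However, the cell dose has since been raised, and section 10.4's own one-sided 95% limit after no events in 12 is 22%.

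**Conclusion.** The individual stopping rule is inconsistent. Section 5.5.1 ends treatment without exception for a class of events that 9.1.5 (non-local, thought related) and 9.1.4.2 (local, when judged related) handle with a hold until consultation, and the protocol does not rank the sections. The conclusion that 5.5.1 is permanent rests on its heading and on its routing of participants to Visit 23.

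Three stronger readings might be inferred, and the documents do not support them:

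- **That section 9 expressly allows re-dosing after a related Grade 3 or 4 event.** It does so only by implication.
- **That 9.1.2 and 9.1.3 flatly contradict the reaction sections.** Their opening limit can reconcile them with 9.1.4.2 and with infusion reactions under 9.1.5. The remaining difficulty is the breadth of 9.1.5.
- **That the safety endpoint is undermined.** The triggering event is generally counted under either reading.

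The consequence lies in participant management, with effects on who may be replaced and on whether the second leukapheresis is required or discretionary. The contradiction is a matter of text and does not depend on the assumed rates. It should be corrected, but it does not invalidate the design or the analysis.

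**What to change.** Reconcile 5.5.1, 9.1.2, 9.1.3, 9.1.4.2 and 9.1.5:

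1. State one rule for each type of related Grade 3 or 4 event: local reaction, systemic infusion reaction, and other non-local event.
2. Say in 9.1.5 whether it covers infusion reactions only or every related non-local event. Align the heading and text of 9.1.4.2, including whether it depends on relatedness.
3. Put any exception in 5.5.1 itself, or state there that section 9 governs.
4. If consultation is meant only as the step that settles relatedness before 5.5.1 applies, say so.
5. Check that 7.5, 10.4 and 10.5 follow from the chosen rule.

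Which rule is clinically right is for the sponsor to decide. The cost is a protocol wording amendment, with no change to sample size, assessments or analysis.
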